CFRSD	Cystic Fibrosis Respiratory Symptom Diary
CFTR	Cystic fibrosis transmembrane conductance regulator
COPD	Chronic obstructive pulmonary disease
CRF	Case report form
CRP	C-reactive protein
CTCAE	Common terminology criteria for adverse events
CWRU	Case Western Reserve University
DCRU	Dahms Clinical Research Unit
DHQ	Donor History Questionnaire
DLT	Dose limiting toxicity
DMC	Data Monitoring Committee
DMSO	Dimethylsulfoxide
DSMB	Data Safety Monitoring Board
ESR	Erythrocyte sedimentation rate
FBS	Fetal bovine serum
FDA	Food and Drug Administration
FEF_{25%-75%}	Forced expiratory flow
FEV₁	Forced expiratory volume over one second
FVC	Forced vital capacity
GCP	Good Clinical Practice
GGT	Gamma-glutamyl transferase
GM-CSF	Granulocyte-macrophage colony-stimulating factor

GVHD	Graft versus host disease
HIPAA	Health Insurance Portability and Accountability Act of 1996
HIV	Human immunodeficiency virus
hMSC	Human mesenchymal stem cell
hs-CRP	High sensitivity C-reactive protein
ICF	Informed consent form
ICH	International Conference on Harmonization
IL	Interleukin
IRB	Institutional Review Board
IV	Intravenous
LDH	Lactate dehydrogenase
LPS	Lipopolysaccharide
mEq	Milliequivalent
MHC	Major histocompatibility complex
MIP-3α	Macrophage inflammatory protein-3 alpha
MMP-9	Matrix metalloproteinase-9
MPO	Myeloperoxidase
MRSA	Methicillin-resistant Staphylococcus aureus
MSC	Mesenchymal stem cell
MTD	Maximum tolerated dose
NCI	National Cancer Institute
NCRM	National Center for Regenerative Medicine
PBSC	Peripheral blood stem cell
PI	Principal Investigator
QPIT	Quantitative pilocarpine iontophoresis test
RC	Research Coordinator
RSSQ	Respiratory and Systemic Symptoms Questionnaire
SAE	Serious adverse experience
SGOT	Serum glutamic oxaloacetic transaminase
SGPT	Serum glutamate pyruvate transaminase
SOP	Standard operating procedure
TDNCC	Therapeutics Development Network Coordinating Center
TGF-β	Transforming growth factor-beta
TNF-α	Tumor necrosis factor-alpha

PROTOCOL SYNOPSIS

TITLE	A Phase I, Single Center, Open Label, Single Dose, Dose Escalation Study Assessing the Safety and Tolerability of Allogeneic MEsenchymal Stem Cell Infusion in Adults with Cystic Fibrosis-CEASE CF
SPONSOR-INVESTIGATOR	[name].
NUMBER OF SITES	1
RATIONALE	Cystic fibrosis (CF) is a genetically inherited disease which impacts sodium and chloride transport across the epithelium leading to viscous mucus retention, chronic bacterial infection and relentless inflammation in the lung; the main cause of morbidity and mortality in this disease. Although new therapeutics have been promising, new and innovative approaches to controlling inflammation and bacterial burden in the lungs of these patients is important towards minimizing the consequences of the disease and improving survival. We have published pre-clinical studies demonstrating that human allogeneic bone marrow derived human mesenchymal stem cells (hMSCs) may provide a new therapeutic treatment for CF lung disease, attenuating pulmonary inflammation while decreasing bacterial growth and enhancing antibiotic efficiency.
STUDY DESIGN	This will be a prospective, single-center, dose-escalation, open-label interventional study to evaluate the safety and tolerability of allogeneic hMSCs in 15 clinically stable subjects with CF age \geq 18 years. After a two to six week screening period, subjects will have a Baseline visit (Days 1-2) where they will undergo a single intravenous infusion of up to 5×10^6 allogeneic hMSCs/kg of body weight. Infusions will be performed in the Dahms Clinical Research Unit (DCRU) of University Hospitals Cleveland Medical Center. Subjects will be monitored for any infusion related toxicities for 24 hours after the infusion. Subsequent study visits will occur on Days 7, 14, 28, Months 3 and 6 and telephone calls will occur on Days 4 (or 5), 21, 56 and Month 12. Subject safety and tolerability of a single dose of hMSCs will be evaluated at study visits by review of subject diaries, interval history, pulmonary exacerbations (standardized definition in Appendix I), physical examination, spirometry, and analysis of safety laboratories. Special attention will be placed upon detecting pulmonary exacerbations because anti-inflammatory therapies theoretically could suppress the immune system to the point where it leads to increased infectious complications, although MSC therapeutics are proposed to be antimicrobial. In addition to evaluating safety, this study will also explore efficacy end-points for future clinical trials of MSCs in CF including inflammatory biomarkers from blood and sputum. Serum markers (calprotectin, MPO, GM-CSF, IL-1 β , IL-6, IL8, IL-17, and TNF- α) and sputum markers (white cell counts and differentials, IL-1 β ,

	IL-6, IL-8, IL-10, IL-17, GM-CSF, MIP-3 α , TNF- α , and active proteases including neutrophil elastase, α_1 -anti-trypsin, and MMP-9) will be determined at Baseline and on Days 7 and 28 for with-in subject comparison. All subject samples will be archived for future projects. Finally, a diagnostic bone marrow exam will be performed on subjects with CF who consent to undergo the procedure. Bone marrow samples will be banked and used for future translational studies. Study-related procedures are outlined in Appendix II.
PRIMARY OBJECTIVE	To evaluate the infusion-related safety and tolerability of a single allogeneic hMSC infusion in adults with CF.
SECONDARY OBJECTIVES	
 • To explore preliminary evidence for the potential efficacy of MSCs as a new therapeutic to treat CF pulmonary infection and inflammation as measured by 
 ◦ Change in sputum inflammatory markers ◦ Change in serum inflammatory markers • To compare allogeneic MSCs to autologous MSCs in a preclinical model. The potential efficacy of MSCs obtained from CF subjects who agree to undergo the optional bone marrow aspiration will be evaluated in validated animal models.
NUMBER OF SUBJECTS	15 subjects with cystic fibrosis for main study 1-2 healthy volunteer subjects for bone marrow donation only Throughout protocol, “subject” refers to subject with cystic fibrosis unless otherwise specified.
SUBJECT SELECTION CRITERIA	
Inclusion Criteria:
 
 1. Male or female 18 years of age and above 2. Confirmed diagnosis of CF as evidenced by 1 or more clinical features consistent with the CF phenotype and 1 or more of the following criteria: 
 a. Sweat chloride equal to or greater than 60 mEq/L by quantitative pilocarpine iontophoresis test (QIT) b. 2 well-characterized, disease causing mutations in the CFTR gene 3. Clinically stable with no significant changes in health status within 2 weeks prior to screening 4. FEV₁ \geq 40% predicted for age based on the global lung function initiative equations at the screening visit 5. Weight \geq 40 kg at the screening visit 6. Able to perform repeatable, consistent efforts in pulmonary function testing 7. Written informed consent obtained from the subject

	
Exclusion Criteria:
 
 1. Use of an investigational agent within the 4-week period prior to Visit 1 (Day -42 to -10) 2. Chronic daily (>10 mg) or alternate daily (>20 mg on alternate days) use of systemic corticosteroids within the 4 weeks prior to Visit 1 (Day -42 to -10) or initiation of any dosage of systemic corticosteroids within 72 hours prior to Visit 2 (Day 1) 3. Use of hydroxychloroquine or immunosuppressants 4. Initiation of a new antibiotic (oral, IV, and/or inhaled) that is not part of the subject's maintenance regimen for treatment of acute respiratory symptoms within 2 weeks prior to screening through Visit 2 (Day 1) 5. Initiation of any new chronic therapy (e.g., Pulmozyme®, hypertonic saline, Kalydeco®, Orkambi®, high-dose ibuprofen, azithromycin, TOBI®, Cayston®, nebulized colistin, bronchodilators, inhaled corticosteroids, etc.) within 4 weeks prior to screening 6. Active treatment for non-tuberculous Mycobacteria 7. History of a sputum culture positive for a Burkholderia cepacia complex organism in the previous 12 months 8. Current tobacco smoker 9. Oxygen saturation < 92% on room air at Visit 1 (Day -42 to -10) 10. History of pulmonary hypertension 11. SGOT (ALT) or SGPT (AST) > 2.5 times the upper limit of normal at screening, documented biliary cirrhosis, or portal hypertension 12. Total bilirubin concentration > 1.2 mg/dL at screening 13. Creatinine > 1.8 mg/dL at screening 14. Pregnant, breastfeeding, or unwilling to practice birth control between Visit 2 (Day 1) and Telephone Call 3 (Day 56) (acceptable forms of contraception: abstinence, hormonal birth control, intrauterine device, or barrier method plus a spermicidal agent), unless surgically sterilized or postmenopausal 15. Screening hematology with white blood cell count < 4.5 x 10⁹ cells/L, hematocrit < 30%, and platelets < 150 x 10⁹ platelets/L 16. History of invasive cancer requiring systemic therapy 17. History of organ transplantation 18. Currently listed for lung transplantation or having potential to be listed for lung transplantation in the succeeding 12 calendar months from screening 19. Subject unlikely to complete the study as determined by the Investigator
TEST PRODUCT,	Single Infusion of up to 5 x 10 ⁶ allogeneic MSCs/kg of body weight. A

DOSE AND MODE OF ADMINISTRATION	dose escalation using the “3+3” design ¹ will be employed. The three doses are 1×10^6 , 3×10^6 , and 5×10^6 hMSCs/kg. Allogeneic MSCs will be derived from bone marrow aspirates from a healthy donor whose serum tests negative for cytomegalovirus (CMV) antibodies. Healthy donors will undergo tests for infectious disease and screening for 41 common CFTR mutations. In addition, the MSCs will be validated for in vitro and in vivo efficacy and potency using the in vivo murine pre-clinical model of CF lung infection and inflammation.
CONTROL PRODUCT, DOSE AND MODE OF ADMINISTRATION	NA
DURATION OF SUBJECT PARTICIPATION AND DURATION OF STUDY	Subjects will be studied for approximately 13 months Screening: between 10 and 42 days Treatment: 1 day Follow-up: 12 months We anticipate 15 months to recruit subjects (due to the 3+3 safety study design). The last subject in each cohort must finish Visit 5 before enrolling the first subject in the next cohort.
CONCOMITANT MEDICATIONS	For those on alternate month TOBI® or Cayston® therapy, on/off cycles must be timed such that a subject is at the same phase of a cycle at Visits 2-5. Allowed: All routine chronic CF medications. 
Prohibited: Anti-inflammatory medications (hydroxychloroquine, corticosteroids >10mg daily or >20 mg on alternate days) and immunosuppressants between Visits 1 and 5. Changes in chronic treatment of CF (e.g., introduction, dose escalation, or elimination of chronic therapies) between Visits 1 and 5.
SAFETY EVALUATIONS	Dose-limiting toxicities, adverse events, including pulmonary exacerbations; Cystic Fibrosis Respiratory Symptom Diary (CFRSD); Respiratory and Systemic Symptoms Questionnaire (RSSQ); physical examination; assessment of vital signs, including oxygen saturation; spirometry, sputum bacterial culture (quantitative and qualitative); hematology, comprehensive chemistry, erythrocyte sedimentation rate (ESR), high-sensitivity C-reactive protein (hs-CRP), and urinalysis
PRIMARY ENDPOINT	To evaluate safety and tolerability of a single infusion of allogeneic hMSCs as determined by: 
Dose limiting toxicity (DLT): A DLT is triggered by occurrence in the first 24 hours after hMSC infusion of grade ≥ 3 infusion-related allergic toxicities, which include rash, flushing, urticaria, dyspnea, fever $>40^{\circ}\text{C}$ ($>104.0^{\circ}\text{F}$) as scored according to the National Cancer Institute (NCI) Common Terminology Criteria

	
for Adverse Events (CTCAE) version 4.0 (http://evs.nci.nih.gov/ftp1/CTCAE/CTCAE_4.03_2010-06-14_QuickReference_8.5x11.pdf).
 
 • Incidence and severity of adverse events • Number of pulmonary exacerbations (modified Fuch's criteria⁹⁵) • Diary reports (Cystic Fibrosis Respiratory Symptom Diary (CFRSD)) • Changes in subject reported symptoms as captured by the Respiratory and Systemic Symptoms Questionnaire (RSSQ) from Baseline (Visit 2) Day 1 to Baseline (Visit 2) Day 2, Visits 3, 4, 5, 6 and 7 and at times when a pulmonary exacerbation is being considered • Changes in physical examination • Changes in vital signs including oxygen saturation checked throughout infusion • Changes in spirometry (FEV₁ %, FEV₁ (Liters), FEF₂₅₋₇₅) determined 30 minutes, 4 hours, and 24 hours after completion of infusion and from Baseline (Visit 2) Day 1 to Visits 3, 4, 5, 6 and 7 • Change in sputum quantitative microbiology (bacterial colony forming units between Baseline to Day 7 and Day 28) • Changes in hematology, comprehensive chemistry, ESR, hs-CRP, and urinalysis results
SECONDARY ENDPOINTS	
 • Change in blood inflammatory biomarkers from Baseline to Day 7 and Day 28 • Change in sputum inflammatory biomarkers from Baseline to Day 7 and Day 28
OTHER EVALUATIONS	
Bone marrow aspiration is optional. CF bone marrow aspirates will be used to assess autologous approaches to MSC therapeutics.
 
Any sputum or serum remaining after the study will be archived for future translational projects.

SAFETY MONITORING	
The Therapeutics Development Network Coordinating Center (TDNCC) Medical Monitoring Group will serve as the medical monitor for this clinical trial. In addition, the Cystic Fibrosis Foundation Data Safety Monitoring Board (DSMB) will establish a Data Monitoring Committee (DMC) to review data relating to safety and efficacy, to conduct and review interim analyses, and to ensure the continued scientific validity and merit of the study, according to the Cystic Fibrosis Foundation Data Safety Monitoring Board Operations Manual and a DMC Charter established for this protocol. There will be 3 interim review(s) conducted by the DMC for the purpose of monitoring study conduct and assessing subject safety.

RATIONALE FOR NUMBER OF SUBJECTS	This is a single center Phase I study. Enrollment of 15 subjects will be feasible and allow us to ascertain if there are any clinically meaningful infusion-related adverse effects.
---	--

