5 CRITERIA FOR EVALUATION

5.1 Primary Endpoint

The primary outcome will be the safety and tolerability of a single infusion of allogeneic hMSCs. Study participants will be monitored for potential dose limiting toxicities. The dose limiting toxicity (DLT) definition consists of the emergence of infusion-related allergic AEs as well as regimen related toxicities. For this study, a DLT will be considered for the occurrence in the first 24 hours after hMSC infusion of a grade ≥ 3 infusion-related allergic toxicities, which include rash, flushing, urticaria, dyspnea, fever $>40^{\circ}\text{C}$ ($>104.0^{\circ}\text{F}$) as scored according to the National Cancer Institute (NCI) Common Terminology Criteria for Adverse Events (CTCAE) version 4.0. Finally, the CTCAE will be used to assess and grade AE severity, including laboratory abnormalities judged to be clinically significant. In addition to infusion related toxicities, special focus will also be placed upon detecting pulmonary exacerbations since anti-inflammatory therapies theoretically could suppress the immune system to the point where it leads to increased infectious complications. Appendix I lists the criteria for defining a pulmonary exacerbation treated with antibiotics. All AEs encountered during the study period will be captured and graded.

In addition to DLT, safety and tolerability of a single infusion of allogeneic mesenchymal stem cells will also be determined by

- Incidence and severity of AEs
- Number of pulmonary exacerbations (modified Fuch's definition⁹⁵)
- Diary reports (Cystic Fibrosis Respiratory Symptom Diary)
- Changes in subject reported symptoms as captured by the Respiratory and Systemic Symptoms Questionnaire from Baseline (Visit 2) Day 1 to Baseline (Visit 2) Day 2, Visits 3, 4, 5, 6, and 7 and at times when a pulmonary exacerbation is being considered.
- Changes in physical examination
- Changes in vital signs including oxygen saturation checked throughout the infusion

- Changes in spirometry (FEV₁ %, FEV₁ (Liters), FEF₂₅₋₇₅) determined 30 minutes, 4 hours and 24 hours after completion of infusion and from Baseline (Visit 2) Day 1 to Baseline (Visit 2) Day 2, Visits 3, 4, 5, 6 and 7.
- Change in sputum quantitative microbiology (change in bacterial colony forming units between Baseline Day 1 and Day 7 and Day 28)
- Changes in hematology, comprehensive chemistry, erythrocyte sedimentation rate (ESR), high-sensitivity C-reactive protein (hs-CRP), and urinalysis results

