8.3.4 Administration Instructions

The person infusing the cells should wear sterile gloves.

Fresh hMSC will be administered as follows:

hMSCs are infused through a peripheral venous catheter by directly connecting the syringe of cells to the IV tubing via Y-connector.

1. Start infusing IV fluids (normal saline) at the maximal rate (250 ml/hr.).
2. Clean the port of the Y-connector as per hospital protocol.
3. Remove needle from syringe containing the hMSCs.
4. Attach the syringe with hMSCs directly to the in-line Y-connector.
5. Manually clamp the IV tubing leading back to the bag of saline behind the syringe by pinching the tubing between two fingers.
6. Administer a small aliquot (2-3 ml) of the cells from the syringe by slow IV push.
7. Release the IV tubing and allow the normal saline to flush the line for 1-2 minutes.
8. Repeat steps 5 through 7 until all the cells have been infused, completing the infusion over 10-15 minutes.
9. The first post cell infusion rinse of the syringe must now be performed.
10. Manually clamp the IV tubing between the syringe and the study participant by bending the tubing and pinching it between two fingers to draw saline fluid into the syringe, complete filling the syringe.
11. Release the IV tubing leading between the syringe and the study participant.
12. Manually clamp the IV tubing between the bag of saline and the syringe by bending the tubing and pinching it between two fingers.
13. Administer an aliquot (3-5 ml) of fluid from the syringe by IV push.
14. Release the IV tubing and allow the normal saline to flush the line for 30 seconds to 1 minute.
15. Repeat steps 12 through 14 until the syringe is empty. Completing the saline rinse should take approximately 2 minutes.
16. Perform a second post cell infusion rinse of the syringe.
17. Repeat steps 10 through 15.
18. Remove the syringe from the Y-connector port.

19. Administer normal saline through the running IV at a rate of 250 ml/hr. for 4 hours while the study participant is being monitored after the infusion.
20. Document the infusion in a procedure note in the electronic medical record (EMR).

Infusion reactions are documented in the subject's study chart and the principal investigator is notified in the event of severe reactions.

An infusion side-effect checklist is provided to the subject's nurse (a modified version of the standard form used by University Hospitals Cleveland Medical Center Seidman Cancer Center).

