9 STUDY PROCEDURES AND GUIDELINES

A Schedule of Events representing the required testing procedures to be performed for the duration of the study is outlined in Appendix II.

Prior to conducting any study-related activities, written informed consent and the Health Insurance Portability and Accountability Act (HIPAA) authorization must be signed and dated by the subject.

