9.1.9 Intravenous Infusion of hMSCs

Fresh MSCs are infused at Visit 2 (Day 1) from a syringe into a venous catheter followed by a saline wash. After the infusion of cells is complete, 10-ml of a normal saline flush is given immediately and a running IV of normal saline is maintained at 250 ml/hr for 4 hours. Subjects are monitored for 24 hours for infusion-related toxicity. Temperature, blood pressure, heart rate, respiratory rate and oxygen-saturation are measured prior to infusion and at 10 (\pm 5), 20 (\pm 5), 30 (\pm 5), 60 (\pm 15), and 90 (\pm 15) minutes and 2 hours (\pm 15 minutes) and 4 (\pm 15 minutes) hours post-infusion and then every 4 (\pm 15 minutes) hours for the remainder of the 24-hour observation period. Any toxicity is treated at the discretion of the managing physician, and toxicities are reported to the Principal Investigator, IRB, and FDA as appropriate.

MSC infusion has been very well tolerated. Although theoretically of concern, there have been no reported cases of immunosuppression, autoimmunity, cancer, significant lung damage, severe infection, or clinically significant ectopic tissue formation attributable to MSC infusion. MSC infusion could cause infection if the cells are contaminated. Strict aseptic technique during bone marrow aspiration, culture, thawing, and infusion and stringent microbiologic screening minimize this risk. Because of the immunosuppressive effects of MSCs, recipients potentially are at increased risk for infection.

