10.4 Visit 2 (Baseline Visit: Day 1)

1. Perform and record RSSQ prior to any other study procedures
2. Administer and review CFRSD prior to any other study procedures and record any AEs that occurred since Visit 1
3. Review and record interval history
4. Review and record any changes to concomitant medications
5. Review inclusion/exclusion criteria
6. Measure and record weight without shoes
7. Perform and record vital signs, including a blood pressure after the subject has been seated for 5 minutes
8. Perform and record oximetry
9. Collect blood for clinical laboratory tests (comprehensive chemistry panel, ESR, hs-CRP, complete blood count with differential, direct bilirubin and LDH) and vitamin D
10. Collect blood for inflammatory mediators (calprotectin, MPO, GM-CSF, IL-1 β , IL-6, IL-8, IL-17, and TNF- α)
11. Collect urine for clinical laboratory test (urinalysis)
12. Collect urine for pregnancy test prior to infusion
13. Administer 3 puffs of albuterol 15 minutes prior to spirometry if subject is likely to require induction to obtain sputum during the visit
14. Perform and record spirometry approximately 2 hours before hMSC infusion
15. Obtain sputum for clinical laboratory tests (quantitative culture and microbiology) and for research tests (cell count with differential, IL-1 β , IL-6, IL-8, IL-10, IL-17, GM-CSF, MIP-3 α , TNF- α , neutrophil elastase, α_1 -anti-trypsin, and MMP-9). Subjects will be asked to provide sputum via spontaneous expectoration. If a subject is unable to provide sputum spontaneously, then the subject may undergo sputum induction according to the current TDN SOP. Any AEs related to the sputum procedure will be recorded.
16. Temperature, blood pressure, heart rate, respiratory rate and oxygen-saturation are measured prior to the infusion. Subjects should be seated for 5 minutes prior to obtaining vital signs.
17. Perform a complete physical examination
18. Infusion of hMSCs
19. Temperature, blood pressure, heart rate, respiratory rate and oxygen-saturation are measured prior to infusion and at 10 (\pm 5), 20 (\pm 5), 30 (\pm 5), 60 (\pm 15), and 90 (\pm 15) minutes and 2 hours (\pm 15 minutes) and 4 hours (\pm 15 minutes) post-infusion completion and then every 4 (\pm 15 minutes) hours for the remainder of the 24-hour observation period. Subjects should be seated or lying down for 5 minutes prior to obtaining vital signs.

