^f Sputum can be collected by spontaneous expectoration. In those subjects unable to spontaneously expectorate, sputum may be induced by inhalation with 3% hypertonic saline using the current TDN SOP

^g CBC with differential, comprehensive chemistry panel, hs-CRP, ESR, direct bilirubin and LDH

^h Calprotectin, MPO, GM-CSF, IL-1 β , IL-6, IL8, IL-17, and TNF- α

ⁱ IL-1 β , IL-6, IL-8, IL-10, IL-17, GM-CSF, MIP-3 α , TNF- α , neutrophil elastase, α ₁-anti-trypsin, and MMP-9

^j RSSQ should be administered if any increased respiratory symptoms

^k Only if Acute Illness/Early Termination Visit is prior to Visit 5

^l MSCs will be derived from bone marrow samples obtained from healthy volunteers and processed and evaluated according to CCC SOP well in advanced of infusion. CF study staff will inform CCC collaborators when hMSCs will be needed approximately 14 days prior to infusion. CCC collaborators will prepare the proper dose to be infused based upon the weight of the subject with CF

^m Infusion is given by slow IV push and takes less than 30 minutes depending upon the volume to be infused

ⁿ Subjects will be monitored in the CRU for 24 hours after the completion of the infusion. Temperature, blood pressure, heart rate, respiratory rate and oxygen-saturation are measured prior to infusion and at 10 (\pm 5), 20 (\pm 5), 30 (\pm 5), 60 (\pm 15), and 90 (\pm 15) minutes and 2 hours (\pm 15 minutes) and 4 (\pm 15 minutes) hours post-infusion and then every 4 (\pm 15 minutes) hours for the remainder of the 24-hour observation period.

^o On Day 2, spirometry should be performed at 24 (\pm 1) hours after completion of infusion

^p An Acute Illness Visit will be arranged for any subject who experiences any abrupt change in baseline clinical status, between Visit 2 and Visit 5

^q An Early Termination Visit will be completed for any subject terminating study participation between Visit 2 and Visit 7.

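### A primary-endpoint component calls for oxygen saturation and other vital signs throughout the infusion, but no schedule sets a reading between the pre-infusion set and 10 (±5) minutes after completion

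*Combined protocol and SAP*

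**What the plan says.** **Endpoint.** The synopsis includes among the primary-endpoint components "Changes in vital signs including oxygen saturation checked throughout infusion". Section 5.1 has the same item: "Changes in vital signs including oxygen saturation checked throughout the infusion".

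**Schedules.** Section 9 states: "A Schedule of Events representing the required testing procedures to be performed for the duration of the study is outlined in Appendix II". Three places set the readings on the infusion day:

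- Section 9.1.9: "Temperature, blood pressure, heart rate, respiratory rate and oxygen-saturation are measured prior to infusion and at 10" (±5) minutes, then at 20, 30, 60 and 90 minutes, 2 hours and 4 hours post-infusion, and 4-hourly to 24 hours.
- Section 10.4: item 16 sets one pre-infusion set. Item 19 gives the same later times and fixes the clock: "post-infusion completion and then every 4" hours.
- Appendix II note n: the same times, post-infusion.

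**Administration.** Section 8.3.4 has 20 steps, none of which is a vital-sign or oximetry reading. Step 8 gives the duration: "Repeat steps 5 through 7 until all the cells have been infused, completing the infusion over 10-15 minutes". Appendix II note m gives a looser one: "Infusion is given by slow IV push and takes less than 30 minutes depending upon the volume to be infused". Section 8.3.4 also mentions a form: "An infusion side-effect checklist is provided to the" subject's nurse. It ends by setting side-effect monitoring for 24 hours, counted from completion.

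**Analysis.** Section 15.3 reports all measurements at each time point, with changes from Baseline and from the previous time point. Its summary around the infusion names baseline, 30 minutes, 4 hours and 24 hours. It also sends clinically significant vital-sign changes to the adverse-event listings.

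**The concern.** The primary objective is infusion-related safety, and this is the one endpoint component tied to the infusion interval itself. Section 1.3.6.1 gives a reason to look there: the cells are large, they may clump, and pulmonary embolism is named as a possible concern. The same section says no study has reported a change in saturation, so few falls are expected. That record comes from other diseases, however. Section 1.3.2 says no trial of these cells in cystic fibrosis has been published, and inclusion criterion 4 admits subjects with FEV1 down to 40% predicted.

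A statement that saturation did not change during infusion needs readings at the same times in every subject. Without set times, a brief fall during the push could go unrecorded, and whatever readings staff happen to take may not be comparable between dose cohorts. Section 15 promises a separate SAP before the final analysis. That SAP can add a summary, but it cannot supply readings that were not taken.

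The neighbouring spirometry component shows the contrast. Its 30-minute, 4-hour and 24-hour times appear in the endpoint and again in 9.1.7, 10.4, 10.5, Appendix II and 15.3.

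**Working it through.** The plan gives no figure to reproduce. The check sets the endpoint beside the schedules and counts readings.

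**1. Readings by interval**

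| Interval | Readings set | Source |
|---|---|---|
| Before infusion | 1 set | 9.1.9; 10.4 item 16; Appendix II note n |
| Start to completion of infusion | 0 | same schedules; 8.3.4 steps 1–20 |
| First 4 hours after | 10, 20, 30, 60, 90 min, 2 h, 4 h = 7 | 9.1.9; 10.4 item 19; note n |
| Rest of 24 hours | 8, 12, 16, 20, 24 h = 5 | same |

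The total afterwards is 7 + 5 = 12, or 11 if the 24-hour set is counted as the Day 2 visit set. Section 9.1.6 requires oximetry at rest at each visit and adds nothing during the infusion.

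**2. Time from infusion start to the first scheduled reading**

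This is infusion duration plus 10 (±5) minutes, that is, duration plus 5 to 15 minutes.

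- 8.3.4 duration: earliest 10 + 5 = 15 minutes; latest 15 + 15 = 30 minutes.
- Appendix II note m: under 30 + 15, so under 45 minutes.

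Any delay between the pre-infusion set and the start of the infusion is additional.

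**3. Does the interval depend on dose?**

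Note m says duration depends on volume. Section 8.3 fixes the product at 4 × 10⁶ cells/ml, so:

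- 1 × 10⁶/kg ÷ 4 × 10⁶/ml = 0.25 ml/kg
- 5 × 10⁶/kg ÷ 4 × 10⁶/ml = 1.25 ml/kg

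That is a fivefold range. At an assumed 70 kg (the weight implied by the 70 to 350 × 10⁶ cells in 1.3.4.1) the volumes are 17.5 ml and 87.5 ml. Note m therefore allows longer infusions at higher doses. This affects how any new readings should be summarised.

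**4. Entries added by a 5-minute schedule plus completion**

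| Duration | Readings | Per subject | × 15 subjects |
|---|---|---|---|
| 10 min | 5, 10 (completion) | 2 | 30 |
| 15 min | 5, 10, 15 (completion) | 3 | 45 |
| Just under 30 min | 5, 10, 15, 20, 25, completion | 6 | 90 |

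A longer infusion gives more readings. The lowest of more readings tends to be lower by chance alone, so comparing minima could make a high-dose cohort look worse with no true effect. Change at fixed times common to all cohorts avoids this.

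**The case against.** The case for treating this as a small wording matter has several sound parts.

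- **Staff are already told to check.** The endpoint wording itself says so. The nurse's checklist (8.3.4) and the research-unit flow sheets (16.7) may hold readings, but neither is in these documents. A reader might infer that subjects go unmonitored during the push, and the documents do not support that. They show only that no time or frequency is set.
- **Observed changes have a reporting route.** Section 15.3 lists clinically significant vital-sign changes, and adverse events are captured from consent. This stands, but it depends on someone having observed and recorded the change.
- **Persistent falls would be caught** at 10, 20 and 30 minutes after completion. This stands, and it limits the gap to brief falls and to the description of the infusion period.
- **The risk is limited by entry criteria and prior experience.** Exclusions 9 and 10 remove subjects with saturation below 92% on room air or a history of pulmonary hypertension. Section 1.3.4.3.2 reports 43 subjects given 1–5 × 10⁶ cells/kg with no infusion-related toxicity. Section 1.3.4.1 reports the same absence in older COPD subjects, at a fixed 100 × 10⁶ cells. This lowers the expected frequency but does not supply the missing data in cystic fibrosis.
- **The endpoint may mean the infusion visit loosely.** If so, rewording it to before and after infusion would restore consistency. It would also give up inexpensive data on the very interval the trial sets out to describe.

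**Conclusion.** The mismatch is real and worth fixing. A named primary-endpoint component has 0 scheduled readings in the interval it names, and the first scheduled reading comes 15–30 minutes after infusion start (under 45 on Appendix II's duration). The result is no standardised in-infusion data for that component. This rests on the visible text and on reading post-infusion in 9.1.9 and note n as 10.4 does, from completion.

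Three stronger conclusions might be inferred and are not supported:

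- **That DLT counting or escalation is compromised.** Low saturation is not a listed DLT term. Dyspnea is, so a symptomatic event could reach the rule that way, and the data monitoring committee reviews each cohort before the next opens (section 14). The synopsis and 5.1 do not say when the 24-hour DLT window starts. Clarifying that is optional and carries no weight here.
- **That a number of events will be missed.** The documents give no rate of desaturation during infusion, so none can be estimated.
- **That the gap runs to an hour or more at the top dose.** Taking the aliquot and flush steps of 8.3.4 literally gives 30–88 minutes of flush time for 87.5 ml (30 to 44 aliquots of 2–3 ml, 1–2 minutes each). That contradicts the section's own 10–15 minutes and is not relied on.

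**What to change.** **Collection.** In 9.1.9, 10.4 item 19 and Appendix II note n, require saturation, with heart rate, to be recorded at fixed times from the start of the infusion (for example every 5 minutes) and at completion.

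**Analysis.** In 15.3, summarise change from Baseline at the fixed times common to all cohorts (for example 5 and 10 minutes) and at completion. List every fall below a threshold set in advance. Do not compare the lowest value across cohorts. Section 15.2 already defines Baseline as the closest measurement before the infusion, so no new definition is needed.

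**Cost.** Wording in four places. About 2–3 extra flow-sheet entries per subject, at most about 6 (30–45 over 15 subjects, at most 90), and possibly a few more minor events to classify. No change to visits, sample size, DLT definition or escalation.
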